All procedures done during the course of this study are standard treatments for SDH. Patients with SDH that require surgical evacuation who agree to participate, will be randomly assigned either to a surgery group who will continue their course of care after surgery with no further intervention (unless needed as determined by standard of care) and a surgery plus group who, after surgery, will undergo endovascular embolization using standard of care embolization procedures (unless embolization is not indicated for the patient as determined by standard of care). Embolization includes cerebral angiogram with polyvinyl alcohol particle or onyx glue embolization via a catheter inserted in the groin while under general anesthesia. Patients undergoing SDH surgical evacuation are hospitalized on average 2-5 days; randomization and the embolization procedure will take place during the same hospitalization period within 72 hours after surgery. Embolization is a minimally invasive procedure and patients are typically discharged on post procedure Day 1, so the hospital stay will not be increased due to the embolization procedure. Patients will undergo a CT scan within 24 hours after surgery. This scan is standard care and will occur prior to the embolization. Approximately 4-6 weeks after the hospitalization, the patients will undergo a standard follow-up CT scan. Further scans will be done thereafter if clinically indicated. All patients will have the same follow-up care during the course of their hospitalization unless there is a complication.

These procedures, surgery and embolization, are done routinely separately and in combination for treatment of SDH. The research procedure will be the collection of data from these patients to assess whether endovascular embolization following surgical evacuation can reduce the complications of SDH.

b. Describe and explain the study design:

If the study involves multiple conditions where each condition involves different procedures, please provide a table that breaks down the procedures by condition and in chronological order. Include when and where they are performed.

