All data will be managed in a secure format and according to all applicable regulatory guidelines. All medical records information will be entered into the secure drive by the PI or designated study team members. There will be a separate key to link the entries on the data collection form using an assigned study ID# and the patient medical records. The key will be stored on the secure drive. Only the approved investigator or study team members with username/password access will review medical records and the study information that is collected and stored on the secure drive. Women of child-bearing potential are routinely assessed for pregnancy during the pre-operative workup; any with a positive pregnancy test will not be considered for the study, either as treatment or control subjects. Endovascular embolization and imaging are approved and widely used standard treatment options for SDH but carries the risks of groin hematoma, infection, and embolic stroke. In the event of groin hematoma, pressure is applied to the site, evidence of infection would be treated with appropriate antibiotics, and the AU acute stroke protocol would be implemented in the event of an embolic stroke. Study investigators are experienced in performing the procedure and caring for the patients.

If the patient's clinical picture indicates that the embolization procedure is necessary, the patient would not participate in the study. If this determination is made following consent, the patient would be considered a screen failure.

e. Describe the duration of an individual subject's participation in the study and the time involved also include the overall duration of the project:

The duration of subject participation may range from 2 weeks to 3 months following surgical intervention. These are typical follow-up timelines for patients undergoing treatment for SDH. Study information collected from medical records will extend from the time of diagnosis until the completion of follow-up visits.

9. Data and Specimen Management

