The plan might include establishing a data monitoring committee and a plan for reporting data monitoring committee findings to the IRB and the sponsor.

a. Describe the plan to periodically evaluate the data collected regarding both harms and benefits to determine whether subjects remain safe.

A Data Safety Monitoring Board will be established to assess harms and benefits to subjects. The DSMB will evaluate safety data every 6 months during the trial and at the reporting of any serious adverse event.

b. Describe what data are reviewed, including safety data, untoward events, and efficacy data.

The data collection form and all AEs and SAEs will be reviewed, including whether repeat surgery is needed, length of ICU stay and hospitalizations, and any complications/adverse events that occur.

c. Describe how the safety information will be collected (e.g., with case report forms, at study visits, by telephone calls with participants).

The information will be collected from medical records and entered into the data collection form and/or AE/SAE form.

d. Describe the frequency of data collection, including when safety data collection starts.
 
Data collection, including safety information, will begin as soon as patients are enrolled and will last up to three months post-procedure.

e. Describe who will review the data.
 
Members of the DSMB will include [name] and [name]. Both are board-certified neurosurgeons who have completed CITI training.

f. Describe the frequency or periodicity of review of cumulative data.
 
Every 6 months and at the report of any SAE.

g. Describe any conditions that trigger an immediate suspension of the research.
 
If the embolization procedure is associated with statistically significant increased risks to the subject

11. Withdrawal of Subjects

N/A

a. If applicable, describe anticipated circumstances under which subjects will be withdrawn from the research without their consent.
 
Physicians may determine that it is not in the best interest of the patient to undergo the embolization procedure; the patient would be removed for their safety. The patient may also be removed from the study if the physicians determine that another type of treatment would be more beneficial.
	 N/A

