
b. If applicable, describe any procedures for orderly termination.
 
The procedure would not be done.
	 N/A

c. If applicable, describe procedures that will be followed when subjects withdraw from the research, including partial withdrawal from procedures with continued data collection.
 
Subjects may choose to discontinue their participation in the study at any time by notifying the PI. To withdraw from the study individuals are asked to send a written letter to the PI. Data collection for the subject will stop, but data already collected will continue to be used. Subjects may, at any time, change their mind and decide not to have the embolization procedure by letting the study doctors know their wishes. If the embolization procedure is not done, the patient will be included in the analysis as they were randomized.
	 N/A

12. Risks to Subjects

a. List the reasonably foreseeable risks.

There is a potential risk in breach of confidentiality. Endovascular embolization is an accepted standard of care treatment for subdural hematoma but carries the additional risk of groin hematoma, infection, and embolic stroke. The risks of the procedure will be addressed with subjects randomized to the procedure. Control subjects will have no further risks associated with participation.

b. If applicable, describe any costs that subjects may be responsible for because of participation in the research.

The patient's insurance will be billed for the endovascular embolization procedure that is standard clinical care. The patient will be responsible for paying for the care they would normally receive for their condition, as well as for all co-pays, deductibles and denied claims. The embolization procedure and the surgery-embolization procedure combination have been standard practice for the last three years and insurance companies typically pay when both procedures are done in a single hospitalization.

N/A

c. If applicable, describe risks to others who are not subjects.

Click here to enter text.

X N/A

13. Potential Benefits to Subjects

Describe the potential benefits that individual subjects may experience from taking part in the research
There is no benefit guaranteed to the subjects. It is hoped that the results of this study will benefit patients in the future.

14. Confidentiality

Describe the procedures for maintenance of confidentiality.

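### Section 11a lets physicians remove patients from the study with no cut-off at randomisation, and the as-randomised sentence in 11c does not clearly cover those removals in either arm

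*Combined protocol and SAP*

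**What the plan says.** Section 11a answers a prompt about subjects withdrawn from the research without their consent. It gives two routes. In the first, physicians decide that "it is not in the best interest of the patient to undergo the embolization procedure; the patient would be removed for their safety". The second is wider: "The patient may also be removed from the study if the physicians determine that another type of treatment would be more beneficial". Neither is tied to a time point, and the second is not tied to an arm.

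Section 11b, on orderly termination, says only: "The procedure would not be done".

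Section 11c covers subjects who withdraw themselves: "Data collection for the subject will stop, but data already collected will continue to be used". It then says subjects may change their mind about embolization, and ends: "If the embolization procedure is not done, the patient will be included in the analysis as they were randomized".

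Other sections bear on this:
- Section 8a excepts some surgery-plus patients from the procedure ("unless embolization is not indicated for the patient as determined by standard of care") and allows controls further intervention if standard of care requires it. On timing it says that "randomization and the embolization procedure will take place during the same hospitalization period within 72 hours after surgery". The post-operative CT comes before embolization.
- Section 8b says controls will not be embolized. Investigators hold the random number list, and no blinding is described.
- Section 8d takes patients judged to need embolization out of the study: "If this determination is made following consent, the patient would be considered a screen failure".
- Section 10d has data collection running from enrolment to as long as three months after the procedure.
- Section 9a compares control and treatment groups but defines no analysis population.

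**The concern.** Randomisation protects the comparison only if the patients analysed are those who were randomised, or if any who drop out do so for reasons unrelated to outcome. Under 11a, a physician who knows the assignment, and may have seen the post-operative CT, can take a randomised patient out of the study.

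The first route works unevenly. Only surgery-plus patients are assigned embolization, so after randomisation only they can be removed as unfit for it; an equally unfit control stays in. If those removed are at higher risk of redo surgery than the rest of their arm, the surgery-plus rate falls and the comparison favours embolization even with no true effect. If they are at lower risk, the bias reverses. The second route can also remove controls; if those are the high-risk ones, the bias is toward no effect. Redo decompression is the outcome the trial is sized on, with 30 per group, so a few patients matter.

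**Working it through.** **1. The rules side by side, after randomisation**

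| Patient | Removal rule | Kept in the analysis? | Redo surgery still collected? |
|---|---|---|---|
| Surgery plus, declines embolization | none needed | Yes, 11c | Not addressed specifically; 10d is general |
| Surgery plus, physician judges unfit | 11a, first route | Only if 11c extends beyond the patient's own change of mind | Not stated after removal |
| Surgery plus, other treatment better | 11a, second route | As above if not embolized; otherwise no rule | Not stated after removal |
| Control, other treatment better | 11a, second route | No rule; 11c concerns an assigned embolization not done | Not stated after removal |
| Control who is embolized | none (8b says it will not happen) | No rule | 10d is general |

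**2. The plan's own figures**

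Inputs from section 9b: control 35%, treatment 5%, alpha 0.05, chi-square test. Sidedness is not stated; two-sided reproduces the table.

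n = [1.960·√(2·p̄(1−p̄)) + z_power·√(p1(1−p1)+p2(1−p2))]² / (p1−p2)², with p̄ = 0.20.

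For 80% power: (1.960·√0.32 + 0.8416·√0.275)² / 0.09 = 26.7, so 27. The other cells also match (31 and 36; 43, 49 and 57 for 35% v 10%). The sample-size table is not in dispute. At 30 per group, power for 35% v 5% is 84.6% by the normal approximation and 88.0% by exact enumeration of the uncorrected chi-square test. The exact method is used below.

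**3. One patient can decide the result**

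Chi-square = N(ad−bc)² / (product of the four margins).
- 10/30 v 4/30: 60·(10·26−4·20)² / (30·30·14·46) = 3.354, p=0.067.
- Drop one surgery-plus redo case, 10/30 v 3/29: 59·(10·26−3·20)² / (30·29·13·46) = 4.536, p=0.033.
- The other direction, 10/30 v 3/30: chi-square 4.812, p=0.028. Drop two control redo cases, 8/28 v 3/30: 3.250, p=0.071.

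These counts were chosen to lie near 0.05.

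**4. Surgery-plus removals with no true effect**

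Assumptions: k of 30 surgery-plus patients removed, each with redo risk r; common rate p0. The remaining surgery-plus rate is (30·p0 − r·k)/(30 − k). For example, p0=0.35, r=0.70, k=3 gives (10.5−2.1)/27 = 31.1%. Entries are the chance of a significant result favouring embolization.

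| p0 | Redo risk of those removed | k=0 | k=2 | k=3 |
|---|---|---|---|---|
| 35% | 35% (average) | 2.4% | 2.7% | 2.5% |
| 35% | 70% | 2.4% | 4.1% | 5.0% |
| 35% | 100% | 2.4% | 5.9% | 8.5% |
| 35% | 0% | 2.4% | 1.7% | 1.2% |
| 20% | 70% | 2.4% | 5.6% | 7.4% |
| 20% | 100% | 2.4% | 8.5% | 13.7% |

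The 20% rate is an assumption inside the 5–30% recurrence range in the Background. Counting both directions, the 35%/70% row moves from 4.8% to 5.6% (k=2) or about 6.3% (k=3).

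**5. Control removals, true rates 35% v 5%**

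The remaining control rate is (10.5 − r·k)/(30 − k). Power is 88% with none removed. Removing 2 or 3 gives 87% for both at average risk, 82% or 79% at 70% risk, and 76% or 70% if all were certain redo cases.

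**The case against.** The strongest reply is that 11a, 11b and 11c form a sequence: a physician decides against embolization, the procedure is not done, and 11c then analyses the patient as randomised. The condition in 11c is passive and does not say whose decision it was. This reading is available. A reader might infer that 11a and 11c flatly contradict each other; the text does not force that. What remains is that 11a is about leaving the research, not only the procedure, and that the sequence does nothing for controls.

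A reader might also infer a plan to exclude patients. The documents do not support that: 11c shows an as-randomised aim, and 8a mentions departures from assigned care in both arms without calling them removals. But 8a gives no analysis rule.

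On follow-up, 10d sets a general collection period, outcomes come from medical records, and the stop-collection sentence in 11c applies to subjects who withdraw themselves. So no rule discards outcomes after a physician removal. Equally, none says that collection continues for someone taken out of the study.

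A further tempting reading is that 8d makes randomised patients screen failures. That term most naturally refers to the time before randomisation, which 8a places after surgery. This is a wording point only.

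Finally, the eligibility criteria already exclude coagulopathy, liver failure and raised creatinine without dialysis in both arms, so later removals may be few. The illustrations rest on assumed numbers and risks, and at average risk the effect is close to nil. All of that stands and limits the size of the point, but it does not close the gap in the rule.

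**Conclusion.** The concern holds as a gap in the rules. As written, 11a permits removal after randomisation for reasons that may relate to prognosis. 11c can be read to keep surgery-plus patients who are not embolized, but does not clearly do so after a physician removal, and it does not cover controls who are removed or embolized.

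The size cannot be fixed from the documents, which give neither a removal rate nor the redo risk of those removed. There is no bias if removal is unrelated to redo risk, and otherwise its direction depends on which arm loses patients and whether they are at higher or lower risk. With 2 or 3 removals at 70% risk, the effect is modest at the design's 35% rate and larger at 20%; only near-certain redo cases give the largest figures. The change should be made because the rule ought not to depend on which case applies. Confidence is medium, because a charitable reading covers part of the gap.

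**What to change.** 1. In 11a, limit removal from the study to before randomisation. Afterwards physicians may stop or change treatment for safety, but every randomised patient in either arm, including any control who is embolized, stays in the assigned group and denominator. Medical-record follow-up for redo decompression continues to the end of planned follow-up unless consent is withdrawn. Word 11c to match.
2. Where possible, judge fitness for embolization in all patients before randomisation, so that unfit patients are excluded from both arms equally.
3. Minor: add the words before randomisation to the screen-failure sentence in 8d.

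The cost is a few sentences and a matching consent-form line on continued record review, with no added visits or procedures. The real downside is dilution. If k of 30 surgery-plus patients are not embolized and keep a 35% risk, the surgery-plus rate is (0.05·(30−k) + 0.35·k)/30: 7% for k=2 and 8% for k=3. Exact power falls from 88% to about 80% or 75%. Step 2 limits that loss.

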The study design will include a surgery group and a surgery plus group. All patients will have been scheduled to undergo surgical evacuation of SDH as standard treatment. These patients will be approached by one of the investigators with information about the study. After consent, the patient will be randomly assigned to either the surgery or the surgery plus group. A random number list will be provided to the investigators to use for assignment of patients to the surgery or surgery plus group. Patients randomized in the surgery plus group will subsequently undergo endovascular embolization within 72 hours after surgery and during their hospital stay. Patients in the surgery group will not undergo

the embolization procedure. CT scans will be performed as described above as standard care for this population. Follow-up care during their hospitalization will be the same for both groups barring a complication. All procedures (surgical evacuation and endovascular embolization) performed are standard treatment options for SDH that are used at our institution and facilities across the country

c. Data Types and Source Records:

Data will be collected from medical records and will include the following: name, medical record number, age, sex, GCS at admission, IPH volume, whether the patient had surgery, length of stay in the ICU and hospital, IPH volume post-operatively from CT scans, anticoagulant use, history of brain trauma, and any complications (AEs or SAEs).

The study information will be entered into spreadsheets and stored on the secure drive provided by Information Technology specifically for the study.

d. Describe the procedures performed to lessen the probability or magnitude of risks

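### Screen failure (Section 8d) and physician removal (Section 11a) are not limited to the time before randomisation, and the as-randomised sentence in Section 11c does not reach a control who is later embolized

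*Combined protocol and SAP*

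**What the plan says.** Five places in the combined protocol and SAP bear on this.

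- **Order of events.** Section 8b: "After consent, the patient will be randomly assigned to either the surgery or the surgery plus group". Section 8a adds that "randomization and the embolization procedure will take place during the same hospitalization period within 72 hours after surgery".
- **Treatment after assignment (Section 8a).** The surgery group "will continue their course of care after surgery with no further intervention (unless needed as determined by standard of care"). The surgery plus group is embolized "unless embolization is not indicated for the patient as determined by standard of care". Neither exception mentions leaving the study.
- **Screen failure (Section 8d).** Where a patient's "clinical picture indicates that the embolization procedure is necessary, the patient would not participate in the study". It continues: "If this determination is made following consent, the patient would be considered a screen failure".
- **Physician removal (Section 11a).** Physicians may decide that "it is not in the best interest of the patient to undergo the embolization procedure; the patient would be removed for their safety". A second ground follows: "The patient may also be removed from the study if the physicians determine that another type of treatment would be more beneficial". Section 11b gives the only termination procedure, which is that embolization is not carried out.
- **Analysis after withdrawal (Section 11c).** When subjects withdraw themselves, collection stops and existing data are kept. Patients may also decline embolization. A patient in whom embolization was not performed is analysed as randomised.

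Sections 8e and 10d set a general chart-collection period: to the end of follow-up visits, and up to three months after the procedure. Section 9a defines no analysis set.

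**The concern.** The window in Section 8d opens at consent and has no stated end. The second ground in Section 11a has no limit of time or arm. Followed as written, both allow a randomised patient to be excluded on clinical judgement. The one sentence that would keep such a patient in the analysis depends on embolization not having been done.

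Reoperation is the outcome on which the trial is sized (Section 9b), with only 30 patients per arm. Patients excluded on judgement may differ in prognosis from those who stay. Losing recurrers from the control arm would shift the comparison against embolization; losing them from the surgery plus arm would shift it towards embolization.

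**Working it through.** **Step 1: which randomised patients are covered.**

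| Randomised patient | Sections 8a, 8d, 11a, 11b | Section 11c | Disposition |
|---|---|---|---|
| Surgery plus, embolization not done | 8a allows omission; 11a may remove; 11b: no procedure | Condition met | Analysed as randomised |
| Control removed, not embolized | 11a may remove | Condition met if read literally; no arm is named | Analysed as randomised, on that reading |
| Control later found to need embolization, and embolized | 8a: intervention, no removal; 8d read literally: screen failure | Condition fails | Not settled |
| Surgery plus, removed after embolization | 11a second ground sets no time limit; 11b points to removal before the procedure | Condition fails | Not settled, but less likely to arise |

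**Step 2: the plan's sample size.** Inputs from Section 9b: 35% versus 5%, alpha 0.05, power 0.80, chi-square test. Two-sided testing is assumed, because it reproduces the table.

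n = [z(0.975)·√(2·p̄·(1−p̄)) + z(0.80)·√(p1(1−p1) + p2(1−p2))]² / (p1−p2)², with p̄ = (0.35 + 0.05)/2 = 0.20

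= [1.960·√0.32 + 0.8416·√0.275]² / 0.30² = (1.1087 + 0.4413)² / 0.09 = 26.7, so 27 per group.

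This matches the table, as do the other five cells (31 and 36; 43, 49 and 57). At 30 per group the normal approximation gives 84.6% power. Exact enumeration of the uncorrected chi-square test gives 88.0%, with a two-sided error of 4.8% at 35% in both arms. The exact figures are the baseline below.

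**Step 3: effect of leaving patients out.** The documents give no removal rate, so an expected k = 1, 2 or 3 of 30 in one arm is an assumption. Let recurrers be R times as likely to be removed as non-recurrers, before any reoperation is recorded. With recurrence probability p = 0.35 in the affected arm:

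rN = (k/30) / (p·R + 1 − p), and rR = R·rN.

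For k = 3 and R = 3: rN = 0.10/1.70 = 0.0588 and rR = 0.1765. The rate among retained controls is 0.35·(1 − 0.1765)/0.90 = 32.0%, against a true 35%.

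Results by exact enumeration (error: 35% in both arms, either arm affected; power: 35% versus 5%, controls removed):

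| k | Error, R = 1 / 2 / 3 | Power, R = 1 / 2 / 3 |
|---|---|---|
| 0 | 4.77% | 88.04% |
| 1 | 5.12 / 5.13 / 5.17% | 87.66 / 86.65 / 86.03% |
| 2 | 5.19 / 5.28 / 5.43% | 87.13 / 84.91 / 83.48% |
| 3 | 5.18 / 5.40 / 5.77% | 86.61 / 83.00 / 80.58% |

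Much of the rise in error is not selection. Non-selective removal of one patient alone moves it from 4.77% to 5.12%, because the test is discrete and the arms become unequal. If only recurrers are removed, error is 5.46, 6.73 and 9.01%, and power 83.43, 77.11 and 69.20%, for k = 1, 2 and 3. That is a limiting case, not an expectation.

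**The case against.** The strongest reply is that an ordinary reading closes most of the gap. Patients are approached once evacuation is scheduled, and randomisation comes after surgery. There is therefore a real interval between consent and randomisation in which Section 8d can operate, and the term screen failure normally belongs there. After randomisation, Section 8a would then govern a control who needs further intervention, with no removal. This reading is plausible, but Section 8d does not state it.

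Three stronger readings are tempting, and the documents do not support them.

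- A reader might infer that every physician-removed patient drops out of the analysis. Section 11c contains an as-randomised commitment. It covers surgery plus patients who miss the procedure and, since it names no arm, literally covers controls removed without embolization. That last reading is somewhat strained, because the preceding sentence concerns patients who decline the procedure.
- A reader might infer that removal after embolization is a routine route out. Section 11b suggests that removal before the procedure was meant.
- A reader might infer that data stop at removal and that the patient is then counted as not reoperated. The stop rule in Section 11c is written for the subject's own withdrawal, Sections 8e and 10d make no exception for removal, and no section states such a scoring rule.

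What stands is the control who is embolized. There Sections 8a and 8d, read literally, give different dispositions, and Section 11c does not decide between them.

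**Conclusion.** The point holds as a minor matter of wording. One case is clearly uncovered (a randomised control later found to need embolization) and a second is possible but less likely (a surgery plus patient removed after the procedure). Under the assumed 1 to 3 removals of 30 in one arm and a selection ratio of one to three, two-sided error is 5.1-5.8% against 4.8%, and power is 87.7% down to 80.6% against 88.0%. The effect becomes material only if several patients are removed and removal is strongly selective.

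A reader might infer that the plan is biased in favour of embolization. The documents do not support a direction: it depends on which arm loses patients and on their prognosis, and no removal rate is given.

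**What to change.** Reconcile Sections 8a, 8d, 11a and 11c on analysis set and follow-up only:

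1. State in Section 8d that screen failure applies only before randomisation.
2. Extend the as-randomised sentence in Section 11c to every randomised patient in either arm, whatever treatment was received.
3. State in Section 11a that a treatment decision is not exit from the study, and that chart collection of reoperation continues over the period in Sections 8e and 10d unless the patient withdraws consent.

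The clinical grounds for giving or withholding embolization stay with the investigators. The cost is protocol wording: outcomes already come from medical records, so no visit or procedure is added, and the sample size is unchanged. The downside is possible dilution of the effect estimate by patients who did not receive their assigned treatment. The change does not say how a patient with no recorded outcome is analysed; Section 9a would need a separate sentence for that.
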